12.2.12.3. Health-Related Quality of Life

EORTC QLQ-C30 instrument data will be scored as described by Aaronson and colleagues (Aaronson et al. 1993). If not already addressed in the EORTC scoring manual (Fayers et al. 2001), descriptive statistics for each EORTC QLQ-C30 scale will be calculated and compared between arms.

EORTC QLQ-BR23 data will be scored as described by the EORTC scoring manual (Fayers et al. 2001).

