The PFS and OS analyses to test the superiority of abemaciclib to placebo in improving PFS and OS time will use the log-rank test stratified by stratification variables. Additional analyses will be performed using the Kaplan-Meier method to estimate the PFS and OS curves and rates, and the Cox proportional hazard model will be used to estimate the PFS and OS HRs and corresponding 95% confidence interval.

Safety:

All safety summaries and analyses will be based on the Safety Population. Patients will be grouped according to treatment received in Cycle 1.

Health Outcomes:

The maximum change from baseline score will be calculated and summarized for BPI “worst pain” and EORTC composite scores. The number and reason for missing and incomplete questionnaires/assessments will be summarized for each instrument and study arm.

Pharmacokinetics:

PK parameters for abemaciclib in plasma (clearance, exposure, volume of distribution, and half-lives) and inter-individual PK variability will be computed using nonlinear mixed effect modeling implemented in NONMEM. If warranted by the data, PK parameters for fulvestrant in plasma and inter-individual variability estimates will also be computed using nonlinear mixed effect modeling implemented in NONMEM.

Pharmacodynamics:

Pharmacodynamic data (such as neutrophil, lymphocytes, or platelets counts in blood) may be analyzed by means of NONMEM and connected to the population PK model for abemaciclib and/or fulvestrant in a PK/pharmacodynamic model.

Tailoring biomarkers:

Summary statistics will include means, medians, corresponding standard errors, quartiles, and ranges. Biomarkers with discrete measures, such as genotype locus, will be summarized in frequency tables. Correlative analyses may be performed to investigate associations between biomarkers and clinical endpoints.

3. Table of Contents

MONARCH 2: A Randomized, Double-Blind, Placebo-Controlled, Phase 3 Study of Fulvestrant with or without Abemaciclib, a CDK4/6 Inhibitor, for Women with Hormone Receptor-Positive, HER2-Negative Locally Advanced or Metastatic Breast Cancer

Section	Page
1. Protocol I3Y-MC-JPBL(g) MONARCH 2: A Randomized, Double-Blind, Placebo-Controlled, Phase 3 Study of Fulvestrant with or without Abemaciclib, a CDK4/6 Inhibitor, for Women with Hormone Receptor-Positive, HER2-Negative Locally Advanced or Metastatic Breast Cancer.....	1
2. Synopsis	2
3. Table of Contents.....	7
4. Abbreviations and Definitions.....	14
5. Introduction	19

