12.2.12. Health Outcome/Quality of Life Analyses

Patient-reported outcomes are measured through paper versions of the following:

- mBPI-sf (modified Brief Pain Inventory, Short Form)
- EORTC QLQ-C30 (The European Organization for Research and Treatment of Cancer Quality of Life Questionnaire Core 30)
- EORTC QLQ-BR23 (The European Organization for Research and Treatment of Cancer Quality of Life Questionnaire Breast cancer)
- EQ-5D 5L (EuroQol 5-Dimension 5 Level)

For each patient with data from baseline and at least 1 other visit, the maximum change from baseline score will be calculated and summarized for BPI “worst pain”, EORTC composite scores. The reason and number of missing and incomplete questionnaires/assessments by visit will be summarized for each instrument and study arm.

Further analysis details will be described in the SAP.

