12.2.12.1. Pain Intensity

Individual pain items on the mBPI-sf (that is, worst, least, average, and current pain) will be described using descriptive statistics by treatment arm. A mixed effects model, repeated measures model may be applied to compare between treatment arms, which will be adjusted for other covariates. Corresponding analyses will also be conducted for the mean of 7 pain interference with function items. If a patient does not complete Questions 5a through 5g on the BPI-sf, the mean score for the 7 pain interference items will be calculated based on those answered questions when at least 4 out of 7 questions were completed (that is, $\geq 50\%$ of the questions were answered).

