- j One or more of these studies [X-ray, CT scan with bone windows, or MRI] is performed locally at baseline (Day -28 to Day -1), between Day 1 and Day 7 of every second cycle beginning with Cycle 3 and continuing through Cycle 13, between Day 1 and Day 7 of every third cycle after Cycle 13, and within 14 days of clinical progression only for patients with bone lesions identified by bone scintigraphy at baseline. To allow flexibility in tumor assessments, imaging conducted up to 3 days prior to Day 1 of the predefined cycles (as early as Day 26 of the prior cycle) will not be considered a protocol deviation. For patients with new lesions identified by post-baseline bone scintigraphy, targeted assessment by X-ray, CT scan with bone windows, or MRI will be performed to confirm findings. For patients who discontinue study treatment without objectively measured progressive disease (PD), continue to evaluate tumor response approximately every 8 weeks for the first 12 months following randomization and thereafter approximately every 12 weeks by the same method used at baseline and throughout the study until the patient has objective disease progression or until study completion. After the patient has objective disease progression, radiologic tests are no longer required and the patient will continue with post-discontinuation follow-up until the patient's death or overall study completion.
- k mBPI-sf, EORTC QLQ-C30, EORTC QLQ-BR23 and EQ-5D 5L should be administered at baseline (Day -14 to Day -1), Cycle 2 Day 1, and then on Day 1 of every second cycle beginning with Cycle 3 and continuing through Cycle 13, on Day 1 of every third cycle after Cycle 13, and at Short-Term Follow-Up. Patients should complete these assessments before extensive interaction with site staff.
- l Skeletal-Related Events include pathological fracture, spinal cord compression, radiation to bone, and surgery to bone.
- m See Pharmacokinetic Sampling Schedule ([Attachment 7](#)).
- n FSH and estradiol levels are required only for women age <60 years and amenorrheic for at least 12 months.
- o A serum pregnancy test is required only for patients receiving ovarian suppression with a GnRH agonist.
- p For Cycle 2 and beyond, the start of a cycle may be delayed up to 7 days for logistical reasons and up to 14 days to allow sufficient time for recovery from toxicity possibly related to a study drug. Refer to Section [9.4.1.1.2](#).

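### The supplied protocol names no longitudinal model for the EORTC scales, although forms are collected almost entirely on treatment and its own PFS assumptions imply unequal follow-up by arm

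*Protocol*

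**What the plan says.** Protocol 6.2 lists pain and symptom burden, measured among others by the QLQ-C30 and QLQ-BR23, among the objectives on which the two arms are to be compared. The analysis text is spread over several places:

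- **12.2.12.3, QLQ-C30.** After scoring, "descriptive statistics for each EORTC QLQ-C30 scale will be calculated and compared between arms". The sentence opens with a condition: it applies only if the matter is not already covered by the EORTC scoring manual.
- **12.2.12.3, QLQ-BR23.** Scoring by the manual. No comparison of its scales is named.
- **12.2.12 and synopsis.** On the worst-pain item and the composite EORTC scores, the plan reads: "For each patient with data from baseline and at least 1 other visit, the maximum change from baseline score will be calculated and summarized". This summary also appears in the synopsis.
- **12.2.12, missing forms.** "The reason and number of missing and incomplete questionnaires/assessments by visit will be summarized for each instrument and study arm". Anything beyond this is deferred to the SAP.
- **12.2.12.1, pain.** "A mixed effects model, repeated measures model may be applied to compare between treatment arms". Covariate adjustment is foreseen.
- **12.2.12.5, EQ-5D.** A mixed-effects analysis of variance is optional, with interest in the time-by-group interaction.
- **12.2.12.6.** Joint modelling of PRO trajectories and event times is optional and exploratory.
- **10.2.1.2.** The EORTC population is every patient with a baseline form and at least one later form.
- **Attachment 1, questionnaire footnote.** "mBPI-sf, EORTC QLQ-C30, EORTC QLQ-BR23 and EQ-5D 5L should be administered at baseline (Day -14 to Day -1), Cycle 2 Day 1". Later forms fall on alternate cycles (3 to 13) and on each third cycle from there, with one more at Short-Term Follow-Up, about 30 days after treatment ends.

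The only SAP text supplied is an addendum on alpha spending for overall survival.

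**The concern.** Progression is a reason to stop treatment (Protocol 7.3.1), and only one form is collected after treatment stops. The patients contributing scores at later cycles are therefore those who have not yet progressed. If the drug delays progression as the design assumes, each arm is thinned at a different rate. The arm that keeps more patients also keeps more who are doing less well. A by-visit comparison of means can then show a quality-of-life difference that is partly selection.

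The maximum change from baseline has a different weakness. The maximum of more observations tends to be larger, so the arm with more visits shows a larger maximum even if nothing differs between the arms.

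Neither summary uses the baseline score as a covariate, so both also give up precision that the collected data would allow. At stake is a secondary between-arm objective; the primary PFS test is not affected.

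**Working it through.** **1. The plan's own figures.** Inputs from Protocol 12.1: control median PFS 6.5 months, HR 0.703, exponential survival, 378 events, 2:1 allocation, 1-sided 0.025, about 630 patients (420 and 210).

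- Experimental median: 6.5 / 0.703 = 9.25 months, a gain of 2.75 months; 1/0.703 − 1 = 42%. Both match the protocol.
- Power: √(378 × 2/3 × 1/3) × |ln 0.703| − 1.960 = 9.165 × 0.3524 − 1.960 = 1.270, and Φ(1.270) = 0.898. This matches the stated 90% or so.

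**2. Share still on treatment.** Assumption: treatment stops only at progression or death. With 28-day cycles, Day 1 of Cycle c falls at t = (c − 1) × 28 / 30.4375 months, and S(t) = 0.5^(t/median).

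| Visit | t (months) | Placebo | Abemaciclib |
|---|---|---|---|
| Cycle 3 | 1.84 | 82% | 87% |
| Cycle 7 | 5.52 | 56% | 66% |
| Cycle 13 | 11.04 | 31% (65 of 210) | 44% (184 of 420) |
| Cycle 16 | 13.80 | 23% | 36% |
| Cycle 19 | 16.56 | 17% | 29% |

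The gap is largest near Cycle 13, at about 13 points. Expected on-treatment post-baseline forms per patient through Cycle 25, found by summing S(t) over the scheduled visits, are 4.7 and 5.8.

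**3. Selection in a by-visit contrast.** Suppose there is no treatment effect on scores, a higher score is better, and score and time on treatment are jointly normal on a latent scale with correlation ρ (assumed; the documents give none). The mean among those remaining is shifted by ρ φ(k)/S, with k = Φ⁻¹(1 − S). At Cycle 13 and ρ = 0.3 the shift is 0.343 SD for placebo and 0.270 SD for abemaciclib, a difference of −0.07 SD. For ρ = 0.1 and 0.5 it is −0.02 and −0.12 SD.

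A separate simulation assumed random intercept SD 17, slope SD 1.2 per month, residual SD 11 and dropout depending on the last score. It gave a spurious Cycle 13 difference of −1.7 to −3.4 points on a 0–100 scale. The score SD there is √(17² + (1.2 × 11.04)² + 11²) = 24.2, so this is −0.07 to −0.14 SD. The two approaches broadly agree.

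**4. Maximum change.** Again with no treatment effect, scores were simulated with equal within-patient correlation r (assumed) on the same schedule, plus the Short-Term Follow-Up form. The expected maximum was higher in the longer-treated arm by 0.10, 0.08 and 0.06 SD for r = 0.3, 0.5 and 0.7.

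**5. Precision.** With baseline-to-follow-up correlation r, the variance of a comparison is proportional to 1 for raw scores, 2(1 − r) for simple change and 1 − r² with baseline as a covariate. For r = 0.5 to 0.7 (assumed), adjustment removes r² = 25% to 49% of the raw-score variance. Against simple change it removes (1 − r)/2, that is 25% at r = 0.5 and 15% at r = 0.7.

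**The case against.** The strongest reply is that the relevant document has not been seen. Section 12.2.12 defers details to the SAP, and the OS addendum refers to a fuller SAP (version 4) that was not supplied. That document may already contain an EORTC model. This stands, and it makes the recommendation conditional.

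Second, the protocol can be read as wanting description only. Section 10.2.1 makes pain the primary health-outcomes goal, the synopsis criterion for the EORTC instruments is to describe symptom changes, and the hierarchical testing in the documents covers PFS and then OS. This lowers the stakes. It does not remove the comparative objective in 6.2, or the between-arm comparison in 12.2.12.3.

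Third, the effect is small. With 65 and 184 patients and SD 24.2, the standard error at Cycle 13 is 24.2 × √(1/65 + 1/184) = 3.5 points, so 1.7 to 3.4 points is about 0.5 to 1.0 standard error. Section 12.2.12.3 also does not say that the comparison is by visit. Both points are fair.

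A reader might go further than the documents allow in four ways:

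- **That baseline is ignored.** It is not: maximum change from baseline is planned, and the EORTC population requires a baseline form. What is missing is baseline as a covariate.
- **That only patients still on treatment are analysed.** The population is not so restricted, and one form is collected after treatment.
- **That missing data are overlooked.** Missing forms are tabulated by reason, visit and arm, and a joint model is allowed for. Neither commits the plan to an adjustment.
- **That pain has a firm model which the EORTC scales were denied.** The pain and EQ-5D models are options only.

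**Conclusion.** The point holds in a limited form. In the supplied documents, the QLQ-C30 comparison rests on descriptive statistics plus a maximum change for composite scores. The QLQ-BR23 has no scale-level comparison, though the composite scores in 12.2.12 may include it. No longitudinal model is named for either. The condition attached to the QLQ-C30 sentence is unclear, because a scoring manual would not be expected to settle a between-arm analysis.

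The planned summaries are open to bias; the documents do not show that they are biased. The size, roughly 0.02 to 0.14 SD for each effect, depends on correlations and variances that the documents do not give, and on treatment stopping only at progression or death. Section 7.3.1 allows other reasons, and discontinuation for toxicity could shrink, widen or reverse the gap; no rate is given. The effect is modest, but the remedy uses data already collected and also improves precision, so the change is worth making.

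**What to change.** First confirm what the main SAP specifies. Unless it already does so:

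- State in 12.2.12.3 that each QLQ-C30 and QLQ-BR23 scale is compared between arms with a repeated-measures mixed model containing baseline score, randomization strata, visit, treatment and treatment-by-visit.
- Limit the contrasts to visits where a stated share of both arms responds. With 25% as an example, and full response from those on treatment, the assumptions above would stop the contrasts at Cycle 13, since the placebo share falls to 23% at Cycle 16.
- Name the joint model of 12.2.12.6 as a sensitivity analysis. The mixed model accounts for dropout explained by recorded scores, but not for dropout driven by deterioration that no form captured. It reduces the bias and cannot be relied on to remove it.
- Keep the descriptive tables, with numbers responding, as support.
- Delete the conditional opening of the QLQ-C30 sentence.

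Under 12.2.2 such a clarification can go in the SAP before the aggregate database is unblinded; a later change is justified in the study report. The cost is one extra model per scale, plus the joint-model sensitivity analysis. No new data are needed and no sample-size figure changes.

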12.2.12.4. Utilization

Utilization data will be summarized descriptively by category across arms (for example, analgesic use, bisphosphonate use, transfusions, radiation, surgery, and hospitalization days), including a frequency table with tabular statistics. For categorical variables, frequency and the corresponding percentage will be derived and measures of central tendency and variability will be calculated for continuous variables by arm. Tests for differences in proportion between treatment groups and between response groups will be performed.

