Patients will be excluded from the study if they meet any of the following criteria: 13) are currently receiving an investigational drug in a clinical trial or participating in any other type of medical research judged not to be scientifically or medically compatible with this study; 14) have visceral crisis, lymphangitic spread, or leptomeningeal carcinomatosis; 15) have a history of central nervous system metastasis; 16) have received prior treatment with chemotherapy (except for neoadjuvant/ adjuvant chemotherapy), fulvestrant, everolimus, or any CDK4/6 inhibitor; 17) have received treatment with a drug that has not received regulatory approval for any indication within 14 or 21 days prior to randomization of study drug for a nonmyelosuppressive or myelosuppressive agent, respectively; 18) have received recent (within 28 days prior to randomization) yellow fever vaccination; 19) have had major surgery within 14 days prior to randomization; 20) have a personal history within the last 12 months of any of the following conditions: syncope of cardiovascular etiology, ventricular tachycardia, ventricular fibrillation, or sudden cardiac arrest; 21) have serious preexisting medical conditions that, in the judgment of the investigator, would preclude participation in this study; 22) have inflammatory breast cancer or a history of any other cancer (except nonmelanoma skin cancer or carcinoma in-situ of the cervix), unless in complete remission with no therapy for a minimum of 3 years; 23) have received an autologous or allogeneic stem-cell transplant; 24) have active bacterial or fungal infection, or detectable viral infection; 25) are pregnant or breastfeeding; or 26) have initiated bisphosphonates or approved RANK ligand (RANK-L) targeted agents (for example, denosumab) < 7 days prior to randomization.

Test Product, Dosage, and Mode of Administration:

Abemaciclib will be supplied by the sponsor to be administered orally, 150 mg Q12H on Days 1 to 28 of a 28-day cycle, plus fulvestrant will be administered 500 mg intramuscularly into the buttocks slowly (1 to 2 minutes per injection) as two 250-mg injections, one in each buttock, on Days 1 and 15 of Cycle 1, then on Day 1 of Cycle 2 and beyond.

Planned Duration of Treatment:

Treatment period: until disease progression or other discontinuation criteria are fulfilled.

Short-term follow-up (postdiscontinuation): 30 days

Long-term follow-up (postdiscontinuation): until death

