The methods of assessment used at baseline must be used consistently for tumor assessment and will be repeated (with the exception of bone scintigraphy) between Day 1 and Day 7 of every second cycle beginning with Cycle 3 and continuing through Cycle 13 (inclusive), between Day 1 and Day 7 of every third cycle after Cycle 13, and within 14 days of clinical progression. For assessment of response *only in patients with bone lesions identified by scintigraphy at baseline*, the method of assessment used at baseline (X-ray, CT scan with bone windows, or MRI) will be repeated between Day 1 and Day 7 of every second cycle beginning with Cycle 3 and continuing through Cycle 13, between Day 1 and Day 7 of every third cycle after Cycle 13, and within 14 days of clinical progression. Bone scintigraphy should be repeated for all patients between Day 1 and Day 7 of every sixth cycle beginning with Cycle 7, when complete response is identified in target disease, or when progression in bone is suspected. For patients with new lesions identified by post-baseline bone scintigraphy, targeted assessment by X-ray, CT scan with bone windows, or MRI will be performed to confirm findings as described in the

Study Schedule ([Attachment 1](#)). To allow flexibility in tumor assessments, imaging conducted up to 3 days prior to Day 1 of the predefined cycles (as early as Day 26 of the prior cycle) will not be considered a protocol deviation.

For patients continuing treatment after study completion, efficacy assessments (frequency and type of assessments) will be at the discretion of the investigator.

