10.1.4. Secondary Efficacy Measures

The following secondary efficacy measures (Table JPBL.10.1) will be collected at the times shown in the Study Schedule (Attachment 1).

Table JPBL.10.1. Secondary Efficacy Endpoints

Endpoint	Definition
Overall Survival (OS)	The time from the date of randomization to the date of death from any cause
Objective Response Rate	The proportion of patients with CR or PR according to RECIST v1.1
Disease Control Rate (DCR)	The proportion of patients with CR, PR, or SD according to RECIST v1.1
Duration of Response (DoR)	The time from the date of first evidence of a confirmed CR or PR to the date of objective progression or death from any cause, whichever is earlier
Clinical Benefit Rate (CBR)	The proportion of patients with CR, PR, or SD \geq 6 months according to RECIST v1.1

Abbreviations: CR = complete response; PR = partial response; RECIST = Response Evaluation Criteria in Solid Tumors; SD = stable disease.

Overall Survival (OS): OS duration is measured from the date of randomization of any study drug to the date of death from any cause. For each patient who is not known to have died as of the data-inclusion cutoff date for a particular analysis, OS will be censored for that analysis at the date of last contact prior to the data inclusion cutoff date (contacts considered in the determination of last contact date include AE date, lesion assessment date, visit date, and last known alive date).

Objective Response Rate: The objective response rate is the percentage of patients with a best response of CR or PR.

Duration of Response (DoR): The DoR time is defined only for responders (patients with a confirmed CR or PR). It is measured from the date of first evidence of CR or PR to the date of objective progression or the date of death due to any cause, whichever is earlier. For clarity, the start date should be determined by the initial assessment of CR or PR, not the date of confirmation of CR or PR. If a responder is not known to have died or have objective progression as of the data inclusion cutoff date scores, duration of response will be censored at the last complete objective progression-free disease assessment date.

Disease Control Rate (DCR): The DCR is the percentage of patients with a best response of CR, PR, or SD.

Clinical Benefit Rate (CBR): The CBR is the percentage of patients with a best response of CR or PR, or SD for at least 6 months.

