10.2.2. Resource Utilization

Investigators will be asked to report the use of concomitant medications (in particular, analgesics, bisphosphonates, and RANK-L targeted agents), blood product transfusions, radiation therapy, surgery, and hospitalization days. Data on neurosurgical blocks will be recorded on the Concomitant Medication and/or surgery eCRF as appropriate. This information should be collected during the study and at the 30-day follow-up visit.

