12.2.13. Safety Analyses

All safety summaries and analyses will be based upon the Safety Population as defined in Section [12.2.1](#).

Overall exposure to study drug, the numbers of patients completing each cycle, and the dose intensity will be summarized using descriptive statistics. The number of patients with any dose adjustment will be presented for entire treatment period as well as for each cycle. The number of patients with dose reductions, dose delays, or dose omissions will also be summarized, as will the reasons for dose adjustments.

Adverse events will be reported using the MedDRA dictionary. Investigators will report a verbatim AE term and a CTCAE v4.0 term and severity for all AEs. For analysis purposes, the following process will be used:

- The CTCAE v4 term reported by the investigator will be mapped to the MedDRA Preferred Term (PT) and System Organ Class (SOC) using the corresponding MedDRA Lower Level Term (LLT), unless the reported CTCAE term is ‘Other – specify.’
- If the reported CTCAE term is ‘Other – specify,’ the MedDRA LLT, PT, and SOC centrally mapped from the verbatim AE term will be used.
- All listings and summaries will use the PT resulting from this process.

Preexisting conditions are defined as adverse events that begin prior to the first dose of study drug.

A treatment-emergent adverse event (TEAE) is defined as an event that first occurred or worsened in severity after baseline. Comparisons of preexisting conditions to on-treatment events at the LLT level will be used in the treatment-emergent computation.

The following summaries will be produced by PT within SOC: preexisting conditions, SAEs, TEAEs, drug-related TEAEs, and procedure-related TEAEs.

The following summaries will be produced by PT within SOC and maximum CTCAE grade: laboratory-based TEAEs, nonlaboratory-based TEAEs, drug-related laboratory-based TEAEs, and drug-related nonlaboratory-based TEAEs.

Reasons for death will be summarized separately for on-therapy and within 30 days of treatment discontinuation.

Hospitalizations and transfusions during the study treatment period or during the 30-day short-term follow-up period will be summarized by treatment group.

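### Resource use is to be tested between undefined response groups formed after randomization; for hospitalization, and plausibly transfusion, unequal time at risk makes the crude test reject too often

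*Protocol*

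**What the plan says.** Protocol Section 12.2.12.4 opens with description: "Utilization data will be summarized descriptively by category across arms". It names analgesics, bisphosphonates, transfusions, radiation, surgery and hospitalization days as examples. It then adds inference: "Tests for differences in proportion between treatment groups and between response groups will be performed".

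The time over which use is counted varies by patient. Section 10.2.2 says of resource use: "This information should be collected during the study and at the 30-day follow-up visit". Section 12.2.13 says: "Hospitalizations and transfusions during the study treatment period or during the 30-day short-term follow-up period will be summarized by treatment group". The Synopsis sets the length of treatment: "Treatment period: until disease progression or other discontinuation criteria are fulfilled".

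Section 10.1.1 schedules the scans "between Day 1 and Day 7 of every second cycle beginning with Cycle 3", and tolerates "imaging conducted up to 3 days prior to Day 1 of the predefined cycles". With 28-day cycles, the first scheduled scan falls about 56 days after Cycle 1 Day 1, or 53 days at the earliest.

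Section 12.2.12.4 does not say what a response group is. The nearest definitions belong to duration of response, and they differ: Section 10.1.4 requires a confirmed CR or PR, whereas Section 12.2.8.2 refers to best response. For the utilization test, the supplied text gives no landmark, common window, person-time denominator or time-dependent response status.

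**The concern.** Response is an outcome of follow-up. A patient who progresses or dies before the first scan can only be a non-responder, and she also has the shortest window in which to be hospitalized or transfused. A responder has, by construction, been observed at least to a scan (guarantee time), and she may then stay on treatment longer because she responded. A test on the proportion with any use mixes both sources of extra exposure with whatever relation response has to the rate of use. A nominally significant result could then be read as a finding about responders when it reflects only how long they were watched.

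**Working it through.** **Inputs from the protocol.** Sections 8.1 and 12.1 give 630 patients randomized 2:1, control median PFS 6.5 months, exponential times, HR 0.703 and 378 events. Section 12.2.2 gives a 2-sided 0.05 level. Sections 10.1.1, 10.2.2 and 12.2.13 give the scan schedule and collection windows.

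**The plan's own figures.** No figure is stated for the utilization tests, so the PFS design was checked to confirm the inputs. z = √(378 × 2/3 × 1/3) × |ln 0.703| − 1.96 = 9.165 × 0.3524 − 1.96 = 1.27, which gives power of 89.8% against the stated approximate 90%. Experimental median: 6.5/0.703 = 9.25 months. Both agree with Section 12.1.

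**Patients who cannot respond.** P(PFS < 56 days) = 1 − exp(−ln 2 × (56/30.4375)/median). This is 17.8% on placebo (median 6.5) and 12.9% on abemaciclib (median 9.25).

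**Simulation with equal use rates.** There were 2,000 trials per setting. Use was counted to the end of treatment (taken as PFS time) plus 30 days and compared by a pooled z-test of ever-use between responders and non-responders. These inputs are assumptions, not document figures:
- response probability 0.08, 0.15 or 0.25 at each of the first three scans, giving 16%, 29% or 44% overall;
- 12-month use probability 10%, 20% or 40%;
- a 24-month cap on follow-up;
- either no effect of response on PFS, or PFS remaining after response multiplied by 1.5.

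Rejection rate of the crude test (no effect / 1.5-fold):

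| Response | Use 10% | Use 20% | Use 40% |
|---|---|---|---|
| 16% | 16.7% / 31.2% | 25.4% / 52.6% | 48.5% / 81.4% |
| 29% | 23.4% / 46.6% | 42.9% / 75.7% | 76.1% / 96.7% |
| 44% | 34.5% / 64.6% | 66.6% / 92.0% | 93.3% / 99.8% |

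With no effect of response on PFS, mean observation is 425 to 433 days in responders and 279 to 326 days in non-responders.

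**Hand check of the middle cell (29% response, 20% use, no effect).** The daily rate is −ln(0.8)/365.25 = 0.000611. Over mean windows of 429 and 309 days, 1 − exp(−rate × days) gives 23.1% and 17.2%. Simulated ever-use is 22.3% and 16.3%, the same gap of about 6 points. With 183 responders and 447 non-responders, the pooled proportion is 0.180, SE = √(0.180 × 0.820 × (1/183 + 1/447)) = 0.0337 and z = 0.060/0.0337 = 1.78. The chance of exceeding 1.96 is Φ(1.78 − 1.96) = 43%, as simulated.

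**Low use.** Further runs with the same arms and medians and no effect of response gave 15% rejection at a hazard of 0.005 per month (12-month use 1 − exp(−0.06) = 5.8%), 42% at 0.02 (21.3%) and 53% at 0.03 (30.2%).

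**Landmark at day 168 (Cycle 7, 6 × 28 days).** Patients were on treatment and free of prior use at the landmark, with response classified by then.
- Proportion test: 4.2% to 5.8% rejection if response does not affect PFS, but 8.4% to 18.3% if it prolongs PFS 1.5-fold.
- Rate per person-time: 4.2% to 5.9% in all 18 settings.

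The simulation error at 5% is √(0.05 × 0.95/2000) = 0.5 points, so the rate comparison holds its level and the landmark proportion test does not.

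**The case against.** Several objections limit the point without removing it.

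- **Coverage.** It is tempting to infer that every category of resource use is biased towards responders. The documents do not support that. Section 9.6.2 generally ties radiotherapy to permanent discontinuation, so its bias may run the other way. Section 9.6.6 and exclusion [26] place the start of bone agents before randomization, so little use accrues afterwards. Section 9.6.1 allows surgery when study treatment makes a tumor operable, so equal rates are not a natural null there. Analgesics were not simulated.
- **The null.** The protocol plans a test of proportions, and in the simulation the proportions do differ, so rejection is correct in that literal sense. This does not rescue the test, because the difference arises from exposure alone.
- **Inputs.** Response and use rates for this population are not in the documents. No single rejection rate is a forecast for this trial.
- **Response after stopping.** Section 10.1.2 continues scans in patients who stop without progression, and Attachment 5 counts best response to progression or new anticancer therapy. The simulation ends treatment at progression, so it ties response to time on treatment more tightly than the protocol does. This stands as a limit on the size.
- **The missing SAP.** Section 12.2.12 defers detail to the SAP. Only the overall survival addendum was supplied; it refers to SAP v4 and does not cover utilization. The groups, window or a landmark could be set there.
- **Consequence.** Utilization is otherwise descriptive and lies outside the PFS/OS hierarchy. A misleading economic statement is possible, but the protocol plans none.

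**Conclusion.** The point holds in a limited form. As written, the test between response groups confounds response with time at risk for outcomes that accumulate over time. This is shown for hospitalization and plausible for transfusion. The cause is guarantee time plus any longer treatment after response, not guarantee time alone.

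The existence of the bias follows from the scan schedule and the collection windows. Its size rests on assumed response of about 16% to 44% and assumed use rates: roughly 15% to 90% false rejection if response does not affect PFS, and more if it does.

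A reader might also infer that a landmark alone cures the problem. It does so only if response does not prolong treatment. Nor does guarantee time from response status touch the comparison between randomized arms in the same sentence, although the arms may differ in exposure for other reasons. The importance is low. A definition or window in the main SAP could settle the matter.

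**What to change.** Preferred: delete the reference to response groups from Section 12.2.12.4 and keep the comparison of randomized arms. This changes one clause and loses nothing on which the primary or key secondary conclusions depend.

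If the comparison is wanted, define the groups, including whether response must be confirmed. Classify response by the Cycle 7 scan among patients still on treatment, count only later use, and compare rates per patient-year. Do not use a simple proportion test after the landmark.

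The cost of the landmark version is the loss of patients who stop before Cycle 7. Under the protocol's PFS assumptions, with 168/30.4375 = 5.52 months, 1 − exp(−ln 2 × 5.52/median) is 44% on placebo and 34% on abemaciclib. Weighted 2:1 that is about 37% of patients, and discontinuation for other reasons would add to it. The result then describes only patients who reach the landmark.

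If the main SAP already contains such a rule, a cross-reference in Section 12.2.12.4 is enough.
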